2.2.6 TERTIARY OUTCOMES

- Use of oxygen therapy, downloaded from POC flash memory, measured in hours at 3 and 6 months
- Reason for cessation of therapy where relevant (patient request, commencement of LTOT, other).
- Oxygen saturation in daily life, measured using a Nonin 3150 Wrist Oximeter during waking hours for 2 consecutive days at 3 and 6 months.

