2.3 INTERVENTION

For the oxygen group, ambulatory oxygen therapy will be delivered using the Inogen One G3 HF POC. Ambulatory air will be delivered using the Inogen One G3 HF POC that has been modified by the manufacturer to deliver only air. The POCs are identical in appearance.

All participants are informed that the aim of using a POC is to assist them to be more active, with fewer symptoms. They are encouraged to use the POC at all times when they are moving about, including walking at home or in the community, during exercise or during other activities. The POC should not be used when sitting still or sleeping. Written and verbal education are provided. Participants are encouraged to use their allocated POC during physical activity for the 6-month study period. The Inogen One G3 HF POC is used at its maximum flow setting of 5 for both groups.

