4.9.1 MAIN ANALYSIS

The primary analysis will use linear mixed models, with site as a random effect. We will compare change from baseline at 3 and 6 months between groups, with the baseline measurement included in the model as a covariate. The treatment effect will be presented as the mean difference between groups with the corresponding 95% confidence interval. Desaturation during 6MWT, although a stratifying factor in the design, will be modelled as a fixed effect.

The assumption of homogeneity of variance will be examined for each outcome by plotting residuals from the model against fitted values. Where right skewness results in heterogeneity of variance, a log transformation will be applied.

Missing data are anticipated for the primary outcome. The primary outcome is assumed to be missing-at-random (MAR), i.e. it is assumed that the probability of 3 month steps/day data being missing may depend on the values of the observed data, but not on the values of the missing data. Important explanatory and auxiliary variables such as age, type of ILD, respiratory function and extent of exertional desaturation are being collected and will be examined to assess the plausibility of the MAR assumption.

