4.12 ANALYSIS OF TERTIARY OUTCOMES

- 4.12.1 Portable oxygen concentrator usage, reported as total hours at 3 and 6 months, and mean hours per day. Differences between randomized groups will be compared.
- 4.12.2 Reason for cessation of therapy where relevant (patient request, commencement of LTOT, other) will be reported as number and percent of randomized group.
- 4.12.3 Oxygen saturation in daily life at 3 and 6 months, measured using a Nonin 3150 Wrist Oximeter during waking hours for 2 consecutive days. Reported as % of monitored time with $SpO_2 \leq 88\%$ during daily life and compared between randomised groups.

These outcomes will be analysed using similar models to those used for the primary and secondary outcomes, depending on whether the data are continuous, binary or counts.

- 4.12.4 We will conduct an exploratory analysis to investigate the impact of portable concentrator usage (mean hours per day) on the primary outcome of mean steps/day using linear mixed models, with POC usage modelled as a random effect.

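### SAP 4.12.4 gives concentrator usage only a random effect, so as worded the model yields no average slope of steps/day on hours of use and no confidence interval for one

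*SAP*

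**What the plan says.** SAP 4.12.4 sets out to "investigate the impact of portable concentrator usage (mean hours per day) on the primary outcome of mean steps/day" by linear mixed models, "with POC usage modelled as a random effect". This is the only role the SAP gives to usage as an explanatory variable. No unit is named over which a usage effect would vary.

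SAP 4.9.1 treats random and fixed as different things. On the one hand, "The primary analysis will use linear mixed models, with site as a random effect". On the other, desaturation on the walk test, "although a stratifying factor in the design, will be modelled as a fixed effect".

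The sentence in 4.12 that refers tertiary outcomes to models similar to the primary and secondary ones stands before 4.12.4 and concerns usage, cessation and saturation as outcomes. The models it points to contain no usage term.

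Usage is a continuous quantity taken from the device (2.2.6: "Use of oxygen therapy, downloaded from POC flash memory, measured in hours at 3 and 6 months").

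**The concern.** The stated aim is the impact of a continuous exposure on steps/day. The natural answer is an average change in steps/day per extra hour of daily use, with its uncertainty. A term that is only random does not provide this, because its mean is fixed at zero and the model estimates how much the effect varies.

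A programmer who follows the text literally could report a variance component, or a fit that stops at a variance of zero, and learn nothing about the direction or size of the association. 4.12.4 is the only analysis in the SAP that relates hours of use to steps, so any statement about use and activity would draw on it. The primary, secondary and safety analyses do not depend on it.

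**Working it through.** The SAP states no figure for 4.12.4, so there is none to reproduce. The wording allows three models, taken in turn below.

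**Reading 1: random slope by site, no fixed slope.** For participant i at site j with usage h:

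`y_ij = x_ij'beta + a_j + b_j*h_ij + e_ij`, with `b_j ~ N(0, tau^2)`

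- Usage is absent from the mean, `E(y_ij) = x_ij'beta`.
- It enters only the covariance of two participants i and k at one site, through `tau^2 * h_ij * h_kj`.
- Replacing h by -h gives `tau^2 * (-h_ij) * (-h_kj)`, the same value. The likelihood is therefore identical and tau cannot show direction. Numerically, the largest difference between the two covariance matrices was 0.
- The predicted b_j do carry a sign. They are shrunken towards zero and are not a population slope with a CI.

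**Reading 2: usage as a grouping factor.** With one visit per participant and all usage values distinct, the usage part of the covariance is `tau^2 * I` and the residual part is `sigma^2 * I`. Only the sum `tau^2 + sigma^2` is estimable. In a simulated set with 220 distinct values, the REML log-likelihood was -1735.812 whether 0%, 25%, 50%, 75% or 95% of the non-site variance was assigned to usage. Rounding usage to 0.1 h (about 52 levels) makes the variance estimable but still blind to sign: median SD 334 for a true slope of +300 and 335 for -300 (60 replicates each).

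**Reading 3: fixed slope plus random slope by site.** This is valid. In one simulated set (true slope 200, 220 participants, 10 sites, residual SD 1500, site SD 200) it gave 197 steps/day per hour/day, 95% CI 39 to 355, the same as a fixed slope alone. In the same data, reading 1 gave a slope SD of 0 and every predicted site slope was 0.

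**Illustration of size.** From SAP 2.5: N = 220, and SD 1582 used as the residual SD. Since 2.5 gives that figure as an outcome SD, 1000 was also run. Assumed, not in the SAP: 10 sites, site SD 300, usage gamma-distributed with mean 2 and SD 1.4 h/day, 40% in one desaturation stratum, one visit. Both models have group, baseline and desaturation fixed and a random site intercept. They are fitted by REML, with intercept and slope uncorrelated in the random-slope model. True slopes are +300 / -300.

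| Scenario | Random only: mean predicted site slope | Fixed slope (SE) |
|---|---|---|
| Base | +122 / -122 | +304 / -305 (77) |
| 5 sites | +194 / -197 | +300 / -303 (77-78) |
| 20 sites | +50 / -56 | +291 / -299 (78) |
| Residual SD 1000 | +204 / -211 | +298 / -305 (49-50) |
| Usage SD 0.8 | +19 / -21 | +305 / -279 (135-136) |
| Usage mean 4, SD 2.5 | +225 / -227 | +301 / -305 (43-44) |

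In the base case (150 trials per sign):

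- The random-only model's median slope SD was 204 / 196, much the same for opposite truths, and it was estimated as zero in 12% / 6% of trials.
- Its mean predicted slope was 122/300 = 41% of the truth. Across scenarios this ran from 19/300 = 6% to 227/300 = 76%.
- The fixed slope's CI coverage was 0.94 / 0.95.
- With a true slope of 0, the fixed slope averaged -4 (SE 78).

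With two visits and a participant random effect (30 replicates each), the fixed slope was +297 / -282 (SE 59) at within-participant correlation 0.5 and +315 / -304 (SE 50) at 0.8.

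**The case against.** The strongest reply is that silence about a fixed term proves little. 4.9.1 does not list randomised group among its fixed effects either, yet group is plainly in that model because a mean difference between groups is reported. An aim to study the impact of usage could likewise imply a mean slope, with the random effect as an addition. This stands as a plausible account of intent. The difference is that usage, unlike group, is expressly assigned a role, and that role is random.

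Three further points have some force:

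- **No promise of a CI.** The CI rule in SAP 4.1 covers treatment effects, so a CI for usage is not strictly promised. The point therefore rests on 4.12.4's own aim.
- **Reading 2 is conditional.** If one usage value per participant spanned both visits, the grouping would act as a participant intercept and be estimable. It would still give no slope.
- **The simulated shrinkage depends on coding.** Centring usage at 2 h/day moved the mean predicted site slope to +183 / -160 (80 replicates per sign), about 57% of the truth, with zero variance in about 1% of fits. The 41% is therefore no forecast for this trial. The algebra holds under either coding.

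Finally, the item is exploratory and has no planned table or figure in Appendix 1. That limits the weight of the point but does not remove it.

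**Conclusion.** The concern holds. As written, 4.12.4 specifies a model that does not answer its own question: under readings 1 and 2 it gives no average slope of steps/day on usage and no interval for one. This follows from the model's form and needs no assumed input. The size of the shrinkage (6% to 76% of a true slope of 300 with uncentred usage) is illustrative and rests on assumed sites, usage distribution and variances.

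Whether the analysis would really be fitted that way is not known, since the authors may have intended reading 3. The consequence is confined to one exploratory item. It should be corrected before that analysis is run, and it does not threaten the trial's main conclusions.

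**What to change.** Replace the closing clause of SAP 4.12.4 with wording such as:

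> POC usage (mean hours/day) will be entered as a fixed continuous covariate in the model of 4.9.1, with randomised group, baseline steps and desaturation as fixed terms and site as a random intercept; a participant random effect is added if both visits are modelled. A random usage slope by site may be added to the fixed slope. The slope will be reported per hour/day with its 95% CI, as a non-randomised association.

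The minimum is the fixed covariate and a named grouping unit for any random slope.

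The label is needed because usage is measured after randomisation and participants are "encouraged to use the POC at all times when they are moving about", so walking more can itself raise hours of use. A fixed slope does not remove that confounding.

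An optional usage-by-group term would separate hours on oxygen from hours on the sham device, which was "modified by the manufacturer to deliver only air". Its SE was about twice that of the pooled slope (156 against 77 in the base case; ratio 2.01 to 2.03 across scenarios), so it may not resolve a moderate difference.

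The cost is SAP wording only. The usage data are already collected from the device.

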APPENDIX 1: PROPOSED TABLES AND FIGURES

Figure 1: Consort flowchart

Table 1: CONSERVE-CONSORT report of trial modifications due to the COVID-19 pandemic

Table 2: Baseline characteristics by randomized group

Table 3: Primary and key secondary outcomes

Figure 2: Longitudinal mean plot of primary outcome, steps per day

Table 4: Adverse events
